#### 3.2 Randomization and Blinding

The randomization will be on a 1:1 basis to supervised versus self-directed rehabilitation, using a validated computer randomization program managed through a secure (encrypted) web-based service by the Oxford Clinical Trials Research Unit (OCTRU). Randomization will use a minimisation algorithm to ensure balanced allocation across the two treatment groups, stratified by centre and initial fracture management (surgical vs non-surgical). The first few participants will be randomised by simple randomization to seed the minimisation algorithm and a probabilistic element introduced to the algorithm to ensure the unpredictability of intervention allocation.

Full details of the randomization are available in AFTER\_RandomizationAndBlindingPlan\_V1.0\_27Jul2022, stored in the confidential statistical section of the Trial Master File (TMF).

Due to the nature of the intervention, it is not possible to blind participants or those delivering the intervention. The local research team at recruiting centres will also not be blinded to the treatment allocation.

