## 3.3 Sample Size

292 (146 per arm) participants providing primary outcome data at 6 months are required to detect a difference of 8 points on the OMAS score with an estimated standard deviation of 21 with 90% power and 5% (2-sided) significance. The minimum clinically important difference for the OMAS selected in surgical trials has usually been 10 points but for this trial of physiotherapy we have chosen a smaller difference of 8 points, which is likely to be clinically important and was supported by our patient advisory group. The chosen standard deviation of 21 is based on the AIM trial (6) (SD 21.7) and the feasibility study data (SD 20.5 based on 32 participants having reached the 6 month time-point). This equates to a standardised effect size of 0.38, a small to moderate effect. In the AFTER feasibility study there was 11% loss to follow-up (those not providing the primary outcome data). In order to allow for potential loss to follow-up of participants in the definitive trial we have inflated the sample size by 15% to aim for a minimum of 344 participants (172 per arm).

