will mostly exclude non-compliers in the intervention arm that may result in estimation bias. CACE looks at compliers in the intervention arm and would-be compliers in the control arm (i.e. the participants in the control arm who would comply to the treatment if they were assigned to the intervention arm) (14). The CACE analysis will be done using a two-stage regression model (14-16):

Stage 1: Predict treatment compliance using treatment allocated. Treatment received (compliance) by participants will be used as an instrumental variable (IV) for treatment allocated. A mixed model, with the independent variable as treatment allocation and the dependent variable as treatment compliance, will run, adjusting for baseline OMAS and initial fracture management. The coefficient estimated for treatment allocation will be used to predict treatment compliance in both intervention and control arm.

Stage 2: Use predicted treatment compliance to represent treatment allocation. A mixed effect model will be run with the dependent variable as OMAS scores and independent variable as predicted treatment compliance and follow-up timepoint interaction. The random effect of the model will be recruitment centre and the model will adjust for fracture management and baseline OMAS score. The Stata command "ivregress" can perform the two-stage analysis together.

For fully adjusted (as per primary outcome analysis) and non-adjusted model, the process will be the same with different variables being adjusted.

The treatment effect for OMAS at 6 months (ITT) and sensitivity analyses results will be presented together in one table for comparison (see table 9 in AFTER\_SAP\_DDT\_V1.0\_18Aug2022). They will be reported alongside 95% confidence intervals and p-values calculated using clustered standard error to account for serial correlations. Mixed model assumptions will be assessed using residual plots. In case we have a skewed variable, we will consider transforming or using bootstrapping methods.

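### The CACE is described both as two separately fitted mixed models and as a one-step ivregress fit; these are different models, and the plan does not say which supplies the interval (a minor correction)

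*SAP*

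**What the plan says.** SAP Section 6.2.1 sets out the CACE in two stages. Stage 1 is a mixed model of compliance on allocation, adjusted for baseline OMAS and fracture management; its allocation coefficient gives predicted compliance in both arms. Stage 2 is fitted separately: "A mixed effect model will be run with the dependent variable as OMAS scores and independent variable as predicted treatment compliance", interacted with timepoint. Of Stage 2 the plan says "The random effect of the model will be recruitment centre and the model will adjust for fracture management and baseline OMAS score". The next sentence reads: "The Stata command 'ivregress' can perform the two-stage analysis together".

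Two further statements in the section bear on the variance. Standard errors are to be clustered, for serial correlation. Bootstrapping is considered only for a skewed variable. The CACE result is tabulated beside the ITT result with a 95% confidence interval and p-value. Section 3.8 calls it supporting evidence for the principal analysis, and Section 6.2.1 lists it among the sensitivity analyses.

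**The concern.** The two descriptions are not the same analysis. The staged text has a centre random effect in Stage 2; ivregress has no random effects. That limit is general knowledge of the command, not something the SAP states. An analyst could follow either description and report a different model and interval.

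The choice matters for the variance. A second-stage model fed with fitted compliance computes its residuals around predicted compliance. The correct instrumental-variable variance uses residuals around the compliance that actually occurred. A joint two-stage least squares (2SLS) routine does this automatically; two models fitted by hand do not. At stake is the width of the CACE interval that readers will set beside the ITT interval.

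**Working it through.** **Inputs from the SAP (Section 3.3).** "292 (146 per arm) participants providing primary outcome data at 6 months are required", "with an estimated standard deviation of 21", for a difference of 8 points, 90% power and two-sided 5% significance. Allocation is 1:1 (Section 3.2).

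**The plan's own figure.** The normal approximation gives 2 × 21² × (1.960 + 1.282)² / 8² = 144.8, so 145 per arm. The t-based calculation gives 146 per arm (power 0.9004), hence 292, and 292 / 0.85 = 343.5, so 344. The sample size reproduces and is not in question.

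**Assumptions, not in the SAP.** Full compliance p in the supervised arm; the difference g in untreated OMAS between compliers and non-compliers; no control-arm crossover (the SAP calls it unlikely).

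**Formula for one visit without covariates.** Let c be the CACE, σ² the variance of the untreated outcome and n the number per arm.

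- Both routes give the same estimate: ITT difference / p.
- 2SLS residuals (around actual compliance) have variance σ² in both arms, so SE = √(2σ²/n) / p.
- Plug-in residuals have variance σ² in the control arm and σ² + p(1−p)[(g+c)² − g²] = σ² + p(1−p)c(c+2g) in the supervised arm.
- Ratio of plug-in SE to 2SLS SE: R = √[1 + p(1−p)c(c+2g) / (2σ²)].

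R is 1 when c = 0. It exceeds 1 when c and c+2g have the same sign and is below 1 when they differ, so the error can go either way.

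**Worked case.** p = 0.70, ITT effect 8, so c = 8/0.70 = 11.43; g = +10; σ² = 441. Then 0.21 × 11.43 × 31.43 = 75.4; 75.4/882 = 0.0855; R = 1.042. The 2SLS SE is √(882/146)/0.70 = 3.51 and the plug-in SE is 3.66. Simulation of this case (6,000 trials) gave 3.52 and 3.67.

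**Range, with ITT effect 8 and σ = 21:**

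| Compliance | c | g = −10 | g = +10 |
|---|---|---|---|
| 60% | 13.33 | −1.2% | +5.9% |
| 70% | 11.43 | −1.2% | +4.2% |
| 85% | 9.41 | −0.7% | +2.0% |

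At 50% compliance (c = 16), g = −15 gives −3.2% and g = +15 gives +9.9%.

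**With baseline adjustment (assumed correlation 0.5; simulation, 2,000 runs per case).**

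- 60% compliance, CACE 8, g = −10: plug-in 3.63, 2SLS 3.70 (−2%).
- 75%, CACE 8, g = 0: 2.88 and 2.85.
- 60%, CACE 16, g = +10: 4.04 and 3.71 (+9%), with coverage 96.6% and 94.3%.
- At a true CACE of 0 the two agree within 0.3%.

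**Does clustering repair it?** No. It changes how residuals are combined over visits, but they are still residuals around predicted compliance. A heteroscedasticity-robust plug-in SE kept the gap (4.02 against 3.69 in the 60%, CACE 16, g = +10 case). A three-visit simulation with participant-clustered standard errors gave differences of about −1% to +6% at 60-85% compliance, with coverage of 0.94 to 0.96.

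**Test of no effect.** In the simple setting the plug-in estimate and its SE are the ITT estimate and its SE, each divided by the same p. Their ratio is the ITT t statistic, so the p-value is not distorted.

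**The case against.** The best defence is that the stages explain the logic and ivregress is the intended implementation. The section also asks for clustered standard errors, and it refers the fully adjusted CACE to the primary model, whose covariate list in Section 6.2.1 has recruitment centre as a fixed effect. Read so, the plan is close to a valid 2SLS analysis. This stands in part: a valid route is available. But the Stage 2 text names a centre random effect, Section 3.8 does the same for the primary model, and nothing says which description governs.

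It is also fair that the closed form and most of the simulations use one visit and no centre effect. The three-visit check narrows that gap, but the size of the error under the exact mixed model has not been shown.

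A reader might infer more than the text supports:

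- That the reported CACE interval will be wrong. This follows only if the plug-in standard error is the one reported, and the SAP does not say that it is.
- That both stages carry a centre random effect. Stage 1 is called a mixed model, but no random effect is named for it.
- That Stage 1 uses everyone randomised and Stage 2 only those with OMAS data. Section 4.2 limits the analysis to participants with a baseline and at least one later outcome, and nothing in Section 6.2.1 says that Stage 1 departs from this.
- That the CACE estimate and p-value are compromised. The working shows that they essentially are not.

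**Conclusion.** The conflict between the two descriptions is real, and the hand-fitted route lacks a valid standard error. The consequence is small. For assumed compliance of 60-85% and complier differences of −10 to +10 points, the standard error is off by about −2% to +6%; it reaches about +10% at lower compliance or larger effects. The direction depends on how compliers differ from non-compliers, so the error cannot be called conservative. It vanishes when there is no effect. Interval width away from the null is all that is affected; the ITT result is untouched, and no decision rule in the SAP uses the CACE interval. This is a minor correction. The size rests on the assumed compliance and complier differences, because the SAP gives neither.

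**What to change.** Make one joint estimator govern and delete the other description. The simpler choice is 2SLS of OMAS on compliance-by-visit, instrumented by allocation-by-visit, with visit effects, the primary model's covariates, centre as fixed effects and standard errors clustered on participant; report the 6-month coefficient. ivregress can fit this. If the centre random effect is to be kept, run both stages together inside a bootstrap that resamples participants, take the interval from it, and drop the ivregress sentence.

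Either wording should name allocation as the instrument, because the Stage 1 text gives that label to treatment received although its regression uses allocation as the predictor. The cost is a few lines of SAP text and code; no new data are needed.

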#### 3.8 Statistical Analysis Outline

The primary analysis population will be the intention-to-treat population (ITT), that is participants will be analysed in the group in which they were randomised regardless of what treatment they received. The analyses will be repeated for the per protocol (PP) population. The per protocol population will exclude participants who did not receive the allocated treatment and participants with major protocol deviations, this will be finalised using blinded data prior to

the final datalock. Standard descriptive statistics will be used to describe the demographics between the treatment groups reporting means and standard deviations or medians and interquartile ranges as appropriate for continuous variables and numbers and percentages for binary and categorical variables. Standard statistical summaries and graphical plots will be presented for the primary outcome measure and all secondary outcome measures.

The OMAS score at 6 months is the primary outcome in this study and will be compared between treatment groups as the dependent variable in a mixed-effects linear regression model including outcome information at intermediate time-points. This model will adjust for stratification factors (initial fracture management; operative or non-operative) and baseline OMAS score. A random effect will be included to account for heterogeneity due to recruitment centres. The treatment effect will be based on adjusted mean differences at 6 months and will be reported together with their 95% confidence intervals.

We will also undertake a Complier Average Causal Effect (CACE) analysis which essentially compares the "compliers" in each group. The CACE analysis will be undertaken using the definition of full compliance in the intervention group – defined as receiving a minimum of 4 physiotherapy sessions. Partial compliance is receiving at least one physiotherapy session (i.e. starting the treatment), which will be used in the per-protocol analysis. This will provide supporting evidence to any findings from the principal analysis. Subgroup analysis by surgical vs non-surgical treatment of the fracture will be undertaken, using a treatment by subgroup interaction term and will be presented using forest plots.

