PROMIS Physical Function (at baseline, 4 and 6 months): assesses the physical function of individuals. A normalised score will automatically be calculated by REDCap built-in programmes. Similar to the analysis for the primary outcome, a mixed effect model with recruitment centre as random effect and adjust for stratification factor (initial fracture management) and baseline PROMIS score. The independent variable of the model will be treatment and follow-up time point interaction. This model will adjust for stratification factors of randomization (recruitment centre and initial fracture management (operative vs non-operative), as well as important prognostic factors of age and sex. Participants who have no access to the online PROMIS computer-adaptive test questionnaire can complete a paper-based PROMIS short form. A sensitivity analysis excluding the PROMIS short form will be conducted to assess

the robustness of the analysis. Results for treatment effect at each of the follow-up timepoints will be presented with 95% confidence intervals and p-values.

Pain (at baseline, 2, 4 and 6 months) will be assessed by both the OMAS and EQ-5D-5L subscale. OMAS pain has 5 categories and ranges from 0-25, the pain decreases as score increases. EQ-5D-5L pain has 5 categories and ranges from 1-5, the pain increases as the score decreases. Both scores will be analysed using a mixed ordinal regression model, adjusting for centre as a random effect and fixed effects for fracture management, their respective baseline score, as well as important prognostic factors of age and sex.

Self-efficacy for exercise (SEE) score (at baseline, 4 and 6 months): ranges from 0-90 with 90 being the most confident and 0 being the least confident for conducting exercise. A mixed effect model with recruitment centre as random effect and adjust for stratification factor (initial fracture management) and baseline SEE score, as well as important prognostic factors of age and sex. The independent variable of the model will be treatment and follow-up time point interaction.

Exercise frequency (at 2, 4 and 6 months): records the frequency of exercise that participants perform in a week, ranges from 7 days to less than 1 day a week. Summary statistics by treatment arm will be presented.

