## 6.3 Missing Data

Missing data will be minimised by careful data management. Missing data will be described with reasons given where available; the number and percentage of individuals in the missing category will be presented by treatment arm. All data collected on data collection forms will be used, since only essential data items will be collected. No data will be considered spurious in the analysis since all data will be checked and cleaned before analysis.

The primary analysis method proposed is reasonably robust to missing at random (MAR) data (18), but this assumption will be investigated by using a pattern mixture model, such as the Stata 'rctmiss' command. The missing data will be assumed to have the same distribution as the observed data, differing by a sensitivity parameter delta. The delta parameter will be the mean shifted value between observed and missing data, measuring the departure from MAR up to one standard deviation from the observed data value. This missing data sensitivity analysis can be used to explore the impact of any potential differential differences in the amount of missing data in the allocated treatment arms.

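### The repeated-measures models specify no participant-level correlation, so the 6-month OMAS contrast is close to a complete-case comparison and the stated MAR robustness fails if dropout depends on earlier scores differently by arm

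*SAP*

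**What the plan says.** - **SAP 3.8 (Statistical Analysis Outline)** describes a mixed-effects regression for 6-month OMAS that also uses the earlier follow-up scores and adjusts for baseline OMAS. On random effects it says only: "A random effect will be included to account for heterogeneity due to recruitment centres".
- **SAP 6.2.1 (Primary outcome analysis)** makes OMAS at every follow-up the dependent variable, as panel data, with a treatment-by-time interaction. Here centre is listed among the fixed effects, and no random effect is named. The results are to come with "p-values calculated using clustered standard error to account for serial correlations". The cluster unit is not given.
- **SAP 6.2.1, CACE stage 2, and SAP 6.2.2** (EQ-5D utility, VAS by reference to it, PROMIS and SEE) again name centre as the random effect. For pain: "Both scores will be analysed using a mixed ordinal regression model, adjusting for centre as a random effect".
- **SAP 6.3 (Missing Data)** states: "The primary analysis method proposed is reasonably robust to missing at random (MAR) data". It adds a delta-based pattern-mixture analysis.
- **SAP 4.2** includes participants with a baseline score and at least one follow-up score.

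No section gives a participant random effect or a residual covariance for the repeated scores. The therapist random effect in 6.5 belongs to a separate sensitivity analysis.

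**The concern.** A repeated-measures model tolerates dropout that depends on earlier scores because it models the correlation between one participant's scores. A participant's 2- and 4-month results then inform the 6-month mean even when the 6-month score is missing. If residuals are independent within participant and treatment-by-time terms are included, that link is absent. The earlier scores can affect the 6-month contrast only through shared covariate and centre effects.

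Clustered standard errors do not restore the link. They change the width of the interval and leave the point estimate where it is. Participants whom section 4.2 admits without a 6-month score would add almost nothing to the primary contrast.

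This matters here because the trial is open-label, the primary outcome is patient-reported, 15% loss is allowed for, and section 6.3 itself foresees different amounts of missing data by arm.

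**Working it through.** **1. The plan's own figure.** Section 3.3 states: "292 (146 per arm) participants providing primary outcome data at 6 months are required", for a difference of 8 points, "with an estimated standard deviation of 21 with 90% power and 5% (2-sided) significance".

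n per arm = 2 × (1.960 + 1.282)² × 21² / 8² = 2 × 10.51 × 441 / 64 ≈ 144.8, so 145. The t-based solution is 145.8, so 146 per arm and 292 in all. With 15% loss, 292 / 0.85 = 343.5, so 344. The figures reproduce. They rest on a single-time-point comparison, so this point does not affect them.

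**2. What the model as written estimates.** With a separate mean for each arm and time, and residuals independent within participant, the fitted 6-month contrast is

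(difference in observed 6-month means) − (baseline slope) × (difference in baseline means among those observed at 6 months).

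Only the slope borrows from 2 and 4 months. This is essentially a complete-case 6-month ANCOVA.

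**3. Bias under one explicit MAR mechanism.** From the SAP: SD 21, 15% missing, 172 per arm. Assumed: correlation between follow-ups r = 0.5 to 0.8, baseline correlation b = 0.4 to 0.5, and 6-month missingness of 25% below and 5% above the 4-month median. Baseline adjustment is taken from section 3.8.

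- Observed fraction: 0.5 × 0.75 + 0.5 × 0.95 = 0.85.
- The mean of each half of a standard normal is ±√(2/π) = ±0.798. Among those observed, the mean 4-month score is shifted by (0.475 − 0.375) × 0.798 / 0.85 = 0.094 SD, and 0.0939 × 21 = 1.97 points.
- Shift in the baseline-adjusted 6-month mean of that arm: 1.97 × (r − b²).

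| b | r | One arm only | Opposite directions (×2) |
|---|---|---|---|
| 0.4 | 0.5 | 1.97 × 0.34 = 0.67 | 1.34 |
| 0.4 | 0.8 | 1.97 × 0.64 = 1.26 | 2.52 |
| 0.5 | 0.5 | 1.97 × 0.25 = 0.49 | 0.99 |
| 0.5 | 0.8 | 1.97 × 0.55 = 1.08 | 2.17 |

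If both arms share the mechanism, the shifts cancel. Without baseline adjustment (b = 0) the ranges are 0.99 to 1.58 and 1.97 to 3.15.

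**4. Simulation of the same mechanism** (3,000 trials per setting, stacked model with independent residuals and no centre effect). Bias was 0.56 to 1.26 for one arm, 0.99 to 2.48 for opposite directions, and at most 0.08 for the same mechanism in both arms. The stacked estimate agreed with the complete-case ANCOVA to within 0.01 point on average. An estimator using the participant's own earlier scores had bias of about 0.1 or less throughout.

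**5. A stronger mechanism, with the centre random effect included.** This used 344 participants, 20 centres, centre ICC 0.02, true effect 8, 15% missing, dropout log-odds changing by 1.0 per SD of the 4-month score, b = 0.4, and 600 trials per setting (Monte Carlo error about 2.3/√600 ≈ 0.09). Mean estimates, centre-only model against the same model with participant covariance:

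| Dropout mechanism | r = 0.5 | r = 0.7 | r = 0.8 |
|---|---|---|---|
| Same in both arms | 7.9 vs 8.0 | 7.7 vs 8.0 | 7.8 vs 8.1 |
| One arm only | 8.8 vs 7.9 | 9.6 vs 8.1 | 9.6 vs 7.8 |
| Opposite directions | 9.7 vs 7.9 | 10.9 vs 8.0 | 11.4 vs 8.0 |

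Here low scorers left the supervised arm, so the bias is upward. In step 3, if they leave the self-directed arm, it is downward. The variance of the centre-only estimate was about 0 to 14% larger.

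**The case against.** The strongest reply is that the SAP omits a participant term but does not exclude one. Section 6.2.1 calls the model mixed, describes the data as a panel and lists centre as fixed. On that reading some other random effect must exist, and the participant is the natural candidate. The clustered-error sentence covers a whole table of results, including the CACE analysis, and robust errors can accompany a participant random effect. This stands to the extent that the text does not prove the analyst will fit the centre-only model. It does not remove the point. The SAP names its random effects several times, never names the participant, and mentions serial correlation only in connection with standard errors. If a participant term is intended it needs writing down; if not, the claim in 6.3 is wrong.

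Second, the sizes depend on the scenario. The documents give no evidence of opposite-direction dropout, and feasibility loss was 11%. That is right, and the near-zero result under a shared mechanism belongs in the account.

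Third, section 6.3 plans a delta analysis up to one SD. One SD at 15% missing in one arm moves the estimate by 21 × 0.15 = 3.15 points, so bias of this order would be probed. But that analysis examines departures from MAR. It does not repair a primary estimate that is biased under MAR.

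A reader might also infer that clustering with about 20 centres inflates the type I error. The documents do not support this: no cluster unit is stated, and serial correlation points to the participant.

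**Conclusion.** The point holds for the models as written. Without participant-level covariance, the 6-month contrast is essentially a complete-case comparison, and two statements are not delivered: the use of intermediate scores (3.8) and the MAR robustness (6.3) when dropout depends on earlier scores differently by arm.

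Under the milder mechanism the bias is roughly 0.5 to 1.3 points for one-arm dropout (6% to 16% of the 8-point target) and 1 to 2.5 points for opposite-direction dropout (12% to 31%). It is larger under stronger mechanisms, with the sign set by who drops out, and near zero if the arms share a mechanism. These sizes rest on assumed correlations and dropout patterns that the SAP does not give.

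Two stronger readings go too far. The primary result is not shown to be biased, because the plan leaves the term unstated and actual dropout is unknown. Nor is MAR robustness lost altogether: the model remains valid when missingness depends only on arm and the model covariates.

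**What to change.** 1. In 6.2.1, specify a within-participant covariance over 2, 4 and 6 months: unstructured, or at least a participant random intercept within centre.
2. Add a participant term to the EQ-5D utility, VAS, PROMIS, SEE and ordinal pain models in 6.2.2.
3. Reconcile centre as random (3.8) with centre as fixed (6.2.1). The EQ-5D and PROMIS paragraphs in 6.2.2 name it both as the random effect and among the adjustment factors.
4. Name baseline OMAS in the 6.2.1 covariate list, as 3.8 does, since the sizes above assume it.
5. If clustered standard errors are kept, state their cluster unit and that they do not replace the participant term. They need not be removed.

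The cost is SAP wording and one extra model term. The sample size does not change, and in the simulations the standard error falls slightly. The change should be made before outcomes are seen by arm, because it determines the primary estimate.
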